4.10.4 Clinical Laboratory Parameters

Hematology and blood chemistry data will be graded according to NCI CTCAE v4.03. The frequencies of the worst severity grade observed will be displayed for each parameter. Laboratory data will also be summarized descriptively based on observed values at each scheduled visit and the change from baseline values at each post-baseline visit.

Baseline is defined as the last evaluation prior to the first dose of study drug. Shift tables from baseline to the worst post-baseline values will be provided for laboratory parameters that have NCI-CTCAE v4.03 toxicity grades. Both scheduled and unscheduled post-baseline values during the treatment period will be considered.

Additionally, the number and percentage of subjects in each treatment group experiencing at least one Grade 3 or 4 event will be tabulated for each NCI CTCAE gradable laboratory test. All clinical laboratory data will be listed by subject and will be structured to permit review of the data over time relative to the start of treatment. Values outside the normal ranges will be flagged and toxicity grades will be displayed for relevant parameters.

Serology testing was not mandatory and discontinued during the study. Serology data collected will be included in the database, but will not be presented in data listings for the CSR.

4.10.5 Vital Signs

Vital sign measurements will be summarized at each infusion, by treatment, using descriptive statistics; change from baseline values will be presented for each timepoint for the Safety Analysis Set. Summary statistics by treatment group will be based on vital sign assessments obtained prior to the first dose of each cycle. Clinically significant post-baseline vital sign findings will be reported as AEs. A by-subject data listing of all vital sign data will be generated.

4.10.6 Physical Examinations

Information on physical examinations will be listed by subject. Clinically significant post-baseline physical examination findings will be reported as AEs.

Neurological assessments will be tabulated using shift tables to categorize subjects according to the change from baseline evaluation to each post baseline visit (Normal, Abnormal – not

clinically significant, Abnormal – clinically significant), for each item in the assessment scale (e.g., mental status, coordination and gait, ..., etc.), by treatment group.

4.10.7 ECOG Performance Status

ECOG performance status scores will be summarized by treatment group. Frequency counts and percentages for the EOT assessment will be presented.

5 INTERIM DATA MONITORING

An independent DMC will review accumulating safety data at scheduled intervals during Part 2 of the study. Attention will focus on the percentage of subjects with SAEs, AEs of special interest, fatal events, and Grade 3 or 4 toxicities, with the severity and relationship to study medication(s) taken into consideration. Details regarding DMC member roles, the frequency of DMC meetings, contents of safety reports, and procedural aspects of DMC meetings will be described in the DMC charter. Excess risk will be determined according to the lower 97.5% lower confidence bound on the difference between incidence rates for Group B (dinutuximab + irinotecan) minus Group A (irinotecan alone). Incidence calculations will depend on the respective numerators and denominators at the time of each interim look. Wilson scores method will be used to calculate confidence limits to ensure that actual coverage is close to the nominal level.

In addition to the safety monitoring, the DMC will review risk-benefit based on investigator-assessed tumor response rates and consider stopping the study early if trends are unfavorable. A short-term endpoint, ORR, will be used for futility assessment. Futility will be based on interim ORR values and the resulting conditional power (CP). The DMC will use CP values to judge the likelihood that the completed trial will demonstrate significantly higher ORR in Group B (dinutuximab + irinotecan) versus Group A (irinotecan alone). The methodology for conditional power estimation is described in Proschan, Lan and Wittes (2006).

No formal interim analysis of OS is planned. However, the number and causes of death in each treatment group will be reviewed by the DMC from a safety perspective. Mortality rates will also be assessed using confidence bounds as described above. A lower limit $>0\%$ would be grounds for stopping the study due to elevated mortality risk associated with dinutuximab.

The planned approach to interim data monitoring will not impact the Type I error rate for the primary efficacy analysis because there is no possibility of stopping for efficacy. Any decision to stop the study would be based on safety issues or futility (the absence of an efficacy signal for tumor response), not a positive effect on survival.

Selected safety and efficacy tables, listings, and figures will be provided for DMC review meetings. Details of the DMC analysis plan will be provided in the DMC Charter.

7 PROGRAMMING CONSIDERATIONS

All tables, data listings, figures (TLFs), and statistical analyses will be generated using SAS[®] Version 9.4 (or higher). Generated outputs will adhere to the following specifications.

7.1 Table, Listing, and Figure Format

7.1.1 General

- 1) All TLFs will be produced in landscape format.
- 2) All TLFs will be produced using the Courier New font, size 9.
- 3) The data displays for all TLFs will have a 1.5-inch binding margin on top of a landscape oriented page and a minimum 1-inch margin on the other 3 sides.
- 4) Headers and footers for figures will be in Courier New font, size 9.
- 5) Legends will be used for all figures with more than 1 variable, group, or item displayed.
- 6) Tables and listings will be in black and white (no color). Figures may be in color.
- 7) Specialized text styles, such as bolding, italics, borders, shading, and superscripted and subscripted text, will not be used in the TLFs. On some occasions, superscripts 1, 2, or 3 may be used (see below).
- 8) Only standard keyboard characters will be used in the TLFs. Special characters, such as non-printable control characters, printer-specific, or font-specific characters, will not be used. Hexadecimal-derived characters will be used, where possible, if they are appropriate to help display math symbols (e.g., μ). Certain superscripts (e.g., cm²) will be employed on a case-by-case basis.
- 9) Mixed case will be used for all titles, footnotes, column headers, and programmer-supplied formats.

7.1.2 Headers

All output will have the following header at the top of the page:

Product: DINUTUXIMAB

Page n of N

Protocol: DIV-SCLC-301

United Therapeutics

All output will have page numbers. TLFs should be internally paginated in relation to the total length (i.e., the page number should appear sequentially as page n of N, where N is the total number of pages in the table).

7.1.3 Display Titles

Each TLF will be identified by a numeral, and the designation (i.e., Table 1) should be centered above the title. A decimal system (Table 14.x.y.z, Figure 14.x.y.z, and Listing 16.2.x.y) should be used to identify TLFs with related contents. The title will be centered in initial capital characters. The analysis set will be identified on the line immediately following the title. The title and table designation will be single spaced. A solid line spanning the margins will separate the titles from the column headers. There will be 1 blank line between the last title line and the solid line.

Table 14.x.y-z

First Line of Title

Second Line of Title if Needed

Safety Analysis Set

7.1.4 Column Headers

- 1) Column headings will be displayed immediately below the solid line described above, in initial upper-case characters.
- 2) For numeric variables, units will be included in column or row heading when appropriate.
- 3) Analysis set sizes will be presented for each treatment cohort in the column heading as (N=xx) (or in the row headings if applicable). This is distinct from the 'n' used for the descriptive statistics representing the number of subjects in the analysis set.
- 4) The order of treatments in the tables and listings will be: (listing only), Dinutuximab + Irinotecan, Irinotecan, Topotecan, and Total [if applicable]).

7.1.5 Body of the Data Display

- 1) Listings will be sorted for presentation in order of schedule, treatment cohort, subject ID, collection day, and collection time.
- 2) If the categories of a parameter are ordered, then all categories between the maximum and minimum category will be presented in the table, even if n=0 for all treatment groups in a given category that is between the minimum and maximum level for that parameter. For example, the frequency distribution for symptom severity would appear as:

Severity Rating	n
Grade 1	20
Grade 2	5
Grade 3	3
Grade 4	5
Grade 5	0

Where percentages are presented in these tables, any counts of 0 will be presented as 0 and not as 0 (0%).

- 3) If the categories are not ordered (e.g., Medical History, Reasons for Discontinuation from the Study, etc.), then only those categories for which there is at least 1 subject represented in 1 or more groups will be included.
- 4) An Unknown or Missing category will be added to the summary of any categorical parameter for which information is not available for 1 or more subjects.
- 5) Unless otherwise specified, the estimated mean and median for a set of values will be presented to 1 more significant digit than the original values, and standard deviations will be presented to 2 more significant digits than the original values. The minimum and maximum will report the same number of significant digits as the original values. For example, for systolic blood pressure:

n	XX
Mean (SD)	XXX.X (X.XX)
Median	XXX.X
Min - Max	XXX, XXX

- 6) Data in columns of a table will be formatted as follows:

- alphanumeric values left-justified;
 - whole numbers (e.g., counts) right-justified; and
 - numbers containing fractional portions decimal-aligned.
- 7) Percentage values will be formatted with 1 digit to the right of the decimal point in parentheses, 1 space after the count (e.g., 7 (12.8%), 13 (5.4%)). Less-than signs (e.g., “<0.1%”) will appear when values are >0.0% and <0.1% (but not equal to 0.0%). Unless otherwise noted, for all percentages, the number of subjects in the analysis set for the treatment cohort who have an observation (i.e., at risk) will be the denominator.
- 8) Tabular displays of data for prior/concomitant medications and all tabular displays of adverse event data will be presented by the drug class, or SOC with the highest occurrence in the MTD cohort(s) (Schedule 1 and Schedule 2 separately), in decreasing order. Within the drug class and SOC, drugs (by ATC code), and adverse events (by PT) will be displayed in decreasing order. If the incidences for multiple terms are identical, they will be sorted alphabetically.
- 9) Missing data will be represented on subject listings as either a hyphen (“-”) with a corresponding footnote (“ - = unknown or not evaluated”), or as “N/A” (footnote “N/A = not applicable”), whichever is appropriate. Missing descriptive statistics or p-values due to non-estimability will be reported as “-” with a corresponding footnote (“- = not estimable”).
- 10) Dates will be formatted in SAS[®]ISO date format yyyy-mm-dd (e.g., “2000-07-01”). Missing portions of dates will be represented on subject listings as blank (e.g., “2000-07”). Dates that are missing because they are not applicable for the particular subject will be presented as “N/A”, unless otherwise specified.
- 11) All observed time values will be presented using a 24-hour clock in hh:mm:ss format (e.g., “01:35:45”, “21:26”). Time values will be reported only if they were measured as part of the study. Vital signs measured relative to dinutuximab infusion are captured on a single date. If clock times run past 24:00 for a given cycle, then add +1 to date.

7.1.6 Footnotes

- 1) A solid line spanning the margins will separate the body of the data display from the footnotes.

- 2) All footnotes will be left justified with single-line spacing immediately below the solid line underneath the data display.
- 3) Informational footnote will begin with “Note:”. Annotation footnotes will begin with an asterisk and other non-numeric symbol. Each new footnote will start on a new line.
- 4) Footnotes will appear on each page. Subject specific footnotes will be avoided.
- 5) Footnotes will be used sparingly, and only if they add value to the table, figure, or data listing. If a data display has more than 4 footnotes, then a cover page may be used to display footnotes, and only those footnotes essential to comprehension of the data will be repeated on each page. Footnotes will not repeat definitions already provided in the SAP.
- 6) The last line of the footnote section will be a standard source line, indicating the data source used by the SAS program that produced the data display, the name of the SAS program, and running date/time.

7.2 Data-Handling Rules

This section describes naming conventions and rules for calculations common to all applicable tables. Some rules specific to a table can be found in the relevant mock-ups.

7.2.1 Unit Conversion to Months

If months are calculated for a duration, the following conversion is used.

- 1) Duration (months): {Duration (days)} / 30.42

7.2.2 Visits

- 1) Relative Study Day: The first day of study treatment is Day 1. A minus (-) sign indicates days prior to the start of study treatment (e.g., Day -5 represents 5 days before start of the study treatment. There is no Day 0.). The relative study day for a specific visit is calculated as (Visit Date – Date of First Dose +1).
- 2) Baseline: For all study variables, baseline is defined as the last measurement obtained prior to the first dose of the study treatment.

7.2.3 Demographics and Baseline Characteristics

- 1) Age = (Date of informed consent–Date of birth + 1) / 365.25 and truncated to complete years.

2) Conversion factors and calculations for height, weight, BMI and BSA:

- a) Height (in cm) = height (in inches) * 2.54
- b) Weight (in kg) = weight (in lbs) * 0.4536
- c) BMI (kg/m²) = Weight(kg)/[Height(m)²]
- d) BSA (m²) = ([Weight (kg) x Height (cm)] / 3600)^{1/2}

3) Geographic regions will be defined as follows:

North America	Canada, US
Western Europe	France, Italy, Spain, UK
Central/Eastern Europe	Bulgaria, Georgia, Hungary, Lithuania, Poland, Slovakia
Russia & Ukraine	Russia, Ukraine
Asia-Pacific	Australia, Hong Kong, India, Korea, Malaysia, Philippines, Taiwan, and Thailand

7.2.4 Prior and Concomitant Medications

- 1) Prior and concomitant medications will be coded and classified using the World Health Organization (WHO) Drug Dictionary (September 2016 or higher). The specific dictionary version will appear in the footnote of the SAS tables/listings.
- 2) Counting rules for prior/concomitant medications: Prior medications include medications that were taken prior to the start of study treatment but stopped before the first dose of study treatment. Concomitant medications during treatment period include medications that started at any time and were taken at any time after the start of study treatment until the 30 days after the end of study treatment.
- 3) Medications missing both start and stop dates, or having a start date prior to 30 days post the last dose of study treatment with the stop date missing, or having a stop date after the start of study treatment with the start date missing, will be counted as concomitant. When partial dates are present in the data, both a partial start date and/or a partial stop date will be evaluated to determine whether it can be conclusively established that the medication either ended prior to the start of study treatment or started after 30 days post the end of study treatment. If the above cannot be conclusively established based on the partial and/or present dates, then the medication will be counted as concomitant.

7.2.5 Safety

- 1) Adverse events will be coded and classified using MedDRA 20.0 or higher. The specific dictionary version will appear in a footnote of the SAS tables/listings.
- 2) Counting rules for AEs: AEs with missing start dates, but with stop dates either overlapping the treatment period or missing, will be counted as treatment-emergent, taking the worst-case approach. Special care will be taken regarding partial dates, applying similar logic to that of the prior/concomitant medications.
- 3) For purposes of flagging individual subject data, laboratory test result abnormalities are defined as values above or below the normal range.

7.2.6 SAS[®] Procedures

This section provides sample SAS[®] code to illustrate statistical analyses specified in the statistical methods section. All computer output from SAS[®] statistical procedures serving as a basis for extracted results (e.g., LIFETEST) will be retained for quality control procedures and will be included in CSR appendices.

Exact 95% confidence interval on ORR/DCR:

```
proc freq;
  by trt;
  table resp / binomial;
run;
```

Median survival time and survival rates with 95% confidence intervals:

```
proc lifetest method=lt intervals =(0 to 24 by 6) outsurv=surv;
  time tte*censor(0);
  strata trt
run;
```

Note: 95% confidence intervals for time intervals (e.g., 3 months, 6 months) will be extracted from the data set SURV.

Cox proportional hazard ratio:

```
proc phreg data=kmvar;
  model aval*cnsr(1) = trtpn/rl;
  strata stln;
run;
```

Stratified log-rank test p-value:

```
Ods output HomTests=pval;  
proc lifetest data=kmvar;  
  time aval*cnsr(1);  
  strata stln / group = trtpn;  
run;
```

Additional SAS[®] code is provided, where necessary, in programming notes for table mock-ups.

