10.9. Efficacy Analysis

10.9.1. OS

OS will be derived as: $(\text{date of death} - \text{date of randomization}) + 1$. Subjects who are alive or permanently lost to follow-up at the cut-off date for the analysis will be censored at the last date the subject was known to be alive.

The primary analysis of OS will be performed using a stratified log-rank test (two-sided, $\alpha=0.05$) to evaluate the difference between survival curves for the dinutuximab combination group versus the irinotecan group (primary comparison). Stratification will be based on the same factor used for randomization (relapse-free period during prior platinum treatment < 3 months vs. ≥ 3 months). Similarly, the stratified log-rank test will be used to compare OS for the dinutuximab combination group versus the topotecan group (exploratory comparison).

Median OS in each treatment group and the corresponding 2-sided 95% confidence interval (CI) will be estimated using the Kaplan-Meier method. Kaplan-Meier estimates of OS distributions will be plotted over time for each treatment group. The hazard ratio and its 95% CIs will be used to summarize the difference in OS distributions.

Sensitivity analyses for the OS endpoint will include an analysis of the subjects in the ITT group who were fully protocol compliant and received at least 80% of the assigned dose of each study

drug. Alternative censoring rules will also be considered to evaluate the robustness of findings to assumptions about dates of death in subjects lost to follow-up.

Cox proportional hazards model will be used to explore the potential impact of stratification factors and other baseline covariates on the primary OS endpoint. The potential influence of the following factors will be examined: age, gender, ethnicity, geographic region of enrolling site, ECOG status, duration of prior response to platinum, ganglioside and PD-L1 expression, and years since diagnosis. Candidate covariates for the multivariate model will be selected using a backward selection process and only variables significant at a 10% level will be considered for the final multivariate model.

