4.9.1 Overall Survival (OS)

OS is defined as duration of time from the date of randomization to the date of the subject's death from any cause. Subjects who are alive or permanently lost to follow-up at the cut-off date for the analysis will be censored at the last date the subject was known to be alive.

The primary analysis of OS will be performed in the ITT set using a stratified log-rank test (two-sided, $\alpha=0.05$) to evaluate the difference between survival curves for the dinutuximab combination group versus the irinotecan group. Stratification will be based on the same factor used for randomization, i.e., the subject's response to prior platinum therapy (relapse-free period during prior platinum treatment < 3 months vs. ≥ 3 months). Similarly, the stratified log-rank test will be used to compare OS for the dinutuximab combination group versus the topotecan group (an exploratory analysis, not part of the hierarchical procedure described above).

Median OS in each treatment group and the corresponding 2-sided 95% confidence interval (CI) will be estimated using the Kaplan-Meier method (Brookmeyer³, 1982). Kaplan-Meier curves for OS distributions will be plotted over time for each treatment group.

In addition, two-sided 95% CIs for the OS rate for each treatment will be constructed at pre-specified time intervals (i.e., 6 months, 12 months, ..., etc.), using the log-log transformation methodology of Kalbfleisch and Prentice (Kalbfleisch⁴, 1980) where the estimated variance of $\log(-\log(\hat{S}(t)))$ is:

$$\tau^2(t) = \sigma^2[\hat{S}(t)\log(\hat{S}(t))]^2$$

The 100 x (1- α)% CI for S(t) is given by:

$$\left[\hat{S}(t)\right]^{\exp(z_{\alpha/2}\tau(t))} \leq S(t) \leq \left[\hat{S}(t)\right]^{\exp(-z_{\alpha/2}\tau(t))}$$

Note that the stratified log-rank test will be used for evaluating the treatment difference. The Kaplan-Meier plots as well as the summary statistics for median OS and the OS rate will be derived from analyses without adjusting for the stratification factor.

The treatment effect of the dinutuximab combination on OS, as compared to irinotecan, will be estimated by the hazard ratio and its 95% CI; the Cox proportional hazards model will be used for this analysis, stratified by the subject's response to prior platinum therapy. Similarly, the hazard ratio and 95% CI comparing the dinutuximab combination group and the topotecan group will be provided.

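### The sample SAS code for median survival uses a 6-month life table where the text specifies Kaplan-Meier (minor, descriptive only)

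*SAP*

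**What the plan says.** Protocol 10.9.1 states: "Median OS in each treatment group and the corresponding 2-sided 95% confidence interval (CI) will be estimated using the Kaplan-Meier method". SAP 4.9.1 repeats that sentence, cites the Brookmeyer-Crowley method for the interval, and treats the curves and the summaries together, as unstratified analyses: "The Kaplan-Meier plots as well as the summary statistics for median OS and the OS rate will be derived from analyses without adjusting". It asks for log-log confidence limits on the OS rates at 6 months, 12 months and so on.

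SAP 7.2.6 introduces its programs as sample "code to illustrate statistical analyses specified in the statistical methods section". One block is headed "Median survival time and survival rates with 95% confidence intervals", and its procedure statement is "proc lifetest method=lt intervals =(0 to 24 by 6) outsurv=surv". The note below it says that "95% confidence intervals for time intervals (e.g., 3 months, 6 months) will be extracted from the data set SURV". The section closes by saying that additional "code is provided, where necessary, in programming notes for table mock-ups"; those mock-ups are not part of the documents.

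The Cox and stratified log-rank programs are separate blocks and do not use `method=lt`.

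**The concern.** `method=lt` requests an actuarial life table. It groups deaths and censorings into the stated intervals, so a median can only be found by interpolating inside an interval six months wide. The Kaplan-Meier estimator uses the individual death times. These are different estimators, yet the code is offered as an illustration of the Kaplan-Meier method in 4.9.1.

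The SAP introduction promises to identify substantial departures from the protocol, and SAP 3.1 lists none. The life table is therefore not presented as a deliberate change.

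The median matters because the design effect is expressed through it: 6 against 8.3 months (SAP 4.2). A table built from this block could show medians that disagree with the Kaplan-Meier figure for the same data. The stake is consistency of descriptive reporting, not inference.

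**Working it through.** **Inputs from the documents.** Medians 6 and 8.3 months, HR 0.725, 306 deaths, two-sided alpha 0.05, 184 subjects in each of Groups A and B, uniform accrual over 10 months plus 14 months of follow-up (SAP 4.2). Cut points 0, 6, 12, 18, 24 (SAP 7.2.6).

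**Assumptions not in the documents.** Time in months, linear interpolation of the life-table median within the interval, and exponential survival, with Weibull shapes k from 0.8 to 1.5 as a check.

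**Design figure.** Schoenfeld power = Φ(√(306/4) × |ln 0.725| − 1.96) = Φ(8.746 × 0.3216 − 1.96) = Φ(0.853) = 80.3%. This reproduces the stated 80% or so, and it does not depend on the median estimator.

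**Large-sample life-table median.** With S(t) = exp(−ln2 × (t/m)^k), and a the start of the interval in which S crosses 0.5:

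life-table median = a + 6 × (S(a) − 0.5) / (S(a) − S(a+6))

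- m = 8.3, k = 1: S(6) = 0.6059 and S(12) = 0.3671, so the median is 6 + 6 × 0.1059/0.2388 = 8.66.
- m = 8.3, k = 0.8, 1.2, 1.5: 8.69, 8.64, 8.60.
- m = 6.0: 6.00 for every k, because the true median lies on a cut point.
- m = 4.0 and 5.0, k = 1: 4.64 and 5.31. Protocol 1.3 gives about 4 to 5 months for resistant or refractory disease, and SAP Table 14.2.1.1.1 reports OS by relapse-free interval.

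**At the planned size.** Simulation with administrative censoring at 24 months and 20,000 trials for k = 1. The actuarial effective number at risk is n − w/2, where w is the number censored in the interval.

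| | Life table | Kaplan-Meier |
|---|---|---|
| Group A, mean median (months) | 6.17 | 6.02 |
| Group B, mean median (months) | 8.66 | 8.34 |
| Mean gain (months) | 2.49 | 2.31 |

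Group A exceeds 6.00 on average because the life-table curve is about twice as steep before month 6 (it falls by 0.50) as after it (by 0.25). The same error in S(6) therefore moves the median further upward than downward.

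- Mean shift in the gain: 2.49 − 2.31 = 0.18 month (0.11 to 0.23 for k = 0.8 to 1.5, 10,000 trials each). The sampling SD of the Kaplan-Meier gain is 1.09 months.
- 5th to 95th percentiles of the shift: −0.59 to +0.93 month. The life-table gain is the smaller one in 34% of trials.
- The two Group B medians differ by at least 0.5 month in 35% of trials (27% to 38% across shapes).
- If the Kaplan-Meier median is instead the first time at which S is 0.5 or less (4,000 trials): Group B 8.68 against 8.30, gain 2.51 against 2.32, life-table gain smaller in 33%, Group B difference of at least 0.5 month in 40%.

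**Survival rates.** With administrative censoring only, nobody is censored before month 14, so the 6- and 12-month rates are identical under both methods. With an assumed 1% per month loss to follow-up they differ by 0.16 to 0.26 percentage point on average. At 18 months with administrative censoring, the mean rates are 12.2% (life table) against 12.5% (Kaplan-Meier) in Group A, and 21.8% against 22.2% in Group B.

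**The case against.** The strongest reply is that the governing method is not in doubt. The code is labelled as a sample serving the methods section, so 4.9.1 ranks above it. The grid suits the OS-rate times in 4.9.1, the note draws only rate intervals from the output, and only the heading connects the block to the median. Further code sits in mock-ups that cannot be seen here.

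The block also cannot run as printed: it names no input data set, and no semicolon appears after the strata variable (possibly a PDF slip). Its variables (`tte`, `censor`, `trt`) differ from those in the other survival blocks (`aval`, `cnsr`, `trtpn`). Harm requires a programmer to repair it, keep `method=lt` against the text, use it for the median, and get past quality control that retains the LIFETEST output.

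All of this stands, and it is why the point is minor. It is a mismatch between code and text rather than a disputed choice of method. It does not remove the contradiction: ranking the text first settles which method is right but leaves the wrong one printed under the median heading. The obvious repair, naming a data set and adding a semicolon, would leave `method=lt` in place.

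It may also be objected that 4.9.1 attaches log-log limits only to the OS rates. It specifies no other transformation for the median interval, and log-log is the default of the product-limit procedure, so using it for both conflicts with nothing in the text.

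**Conclusion.** The point holds and is minor. The sample block headed for median survival contradicts the Kaplan-Meier method that both documents specify. Confidence in the mismatch is high; whether it would ever reach a table is unknown. If it did, under the stated assumptions the Group B median would rise by about 0.3 to 0.4 month on average and the gain by about 0.2 month. The shift in the gain would have no fixed sign in a single trial and would be about one sixth of the sampling SD (0.18/1.09). The primary test, hazard ratio, power, event count, testing hierarchy and plotted curves do not change. The 6- and 12-month rates are essentially unaffected, and the 18-month rates differ by less than half a percentage point on average.

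**What to change.** Replace the block with the default product-limit procedure on the same data set and variables as the Cox and log-rank blocks, for example: `proc lifetest data=kmvar conftype=loglog timelist=(6 12 18 24) reduceout outsurv=surv; time aval*cnsr(1); strata trtpn; run;`

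Take the median and its confidence interval from that output. State that `aval` is in months for this step, derived with the SAP 7.2.1 factor, since that rule is only conditional ("If months are calculated for a duration, the following conversion is used") and the unit in `kmvar` is not given. Align the note on the output data set with the chosen time points. It mentions 3 months, which is not on the present grid, so add that time only if the rate is wanted. Check that the mock-up programming notes use the same code.

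The cost is a few lines of sample code, with no new data and no effect on the primary analysis.
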